10.3. Handling Missing Data

Given that our primary outcome is determined using administrative data, we anticipate minimal missing data for our principal analysis. Therefore, we will use intention-to-treat principles for this analysis.

However, our secondary outcomes rely on self-reported data and therefore there may be considerable missing data points. For the analyses of these outcomes, we will undertake the following procedures for handling missing data:

We will first check the degree and patterns of missingness in the data, based on which we will consider optimal ways of handling missing data to minimise the bias potential. In the presence of missing at random (MAR) given the observed data, we will use methods such as multiple imputation or full information direct maximum likelihood to analyze the missing data.

If the MAR assumption is in doubt, then we will also conduct sensitivity analyses to assess the potential impact that missing not at random (MNAR) may have on the analytic results. Exploration of the sensitivity of conclusion to the MAR assumption may include models which allow for missingness that is not random. These models will include variables that we find to be related to missingness as well as those potentially related to the outcome (including age, sex, baseline medication adherence, comorbidities, household income).

If loss to follow-up is related to the level of the outcome being analyzed, then results obtained under the assumption of independent loss to follow-up may be biased; and in this situation, we will investigate the magnitude of this problem by using measurements taken at previous visits to predict loss to follow-up, and include variables that are determined to predict loss to follow-up in our predictive models in order to satisfy the conditions for the data to be considered MAR, with maximum likelihood techniques being used to estimate parameters. If necessary, we will also examine other approaches in consideration of how robust the results will be and whether they provide appropriately conservative estimates for the outcome analyses.

10.4. Analysis Methods- Primary Outcome

Consistent with an intention-to-treat analysis, we will categorize all participants by their randomization group, regardless of compliance (intention-to-treat), in our primary analysis. For those participants who are no longer actively receiving the self-management intervention or completing follow-up surveys, as permitted by CHREB, we plan to use available health administrative data until the time of death or outmigration from the province.

A Poisson model will test the main effects of the impact of the interventions on the rate of the primary outcome. This technique was chosen as individuals may experience multiple outcomes prior to the end of the study period, therefore we will account for both number of events and varying observation time within the Poisson model (by using an offset to account for losses to follow-up). The likelihood ratio test will test a negative binomial regression model within the Poisson model to examine for the presence of overdispersion. If present, negative binomial models will be used.

10.5. Analysis Methods- Secondary Outcomes

Medication adherence is a binary variable and will be analyzed using log binomial regression (generalized linear models with a log link)—given the likely high prevalence of non-adherence.

EQ5D index scores are continuous and will be analyzed using linear regression.

Medication self-efficacy and concerns will be dichotomized and analyzed using logistic regression.

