6.3. Definition of Quality of Life

The Canadian-specific EQ5D index score will be the primary quality of life measure. For patients who die during the study, subsequent index scores will be given a score of 0, consistent with usual EQ-5D convention (scale is anchored at zero and 1, with zero being dead and 1 being perfect health).

Mixed models will be used to compare EQ-5D index scores over time between the treatment groups for each intervention.

In secondary analyses of EQ-5D index scores, to assess the impact of missing data, we will consider two alternate methods using imputation. Firstly, we will impute missing variables using multiple imputation as noted in section 10.3. We will then use this data to compare the area under the curve of index scores across each intervention group (equivalent to comparing a “QALY” profile for each participant). Secondly, we will use last observation carried forward to impute missing values, and then similarly compare the area under the curve of index scores. Both approaches will test the impact of missingness of data.

7. Trial Population

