7.2. Baseline Characteristics

Baseline characteristics will be reported in a Table using descriptive summary statistics. These will be stratified by group assignment, and t-tests/Chi2 tests will be used to examine for inter-group differences in these characteristics.

8. Data Sources

The main data source for the trial will be the ACCESS trial RedCAP database. This contains participant group assignments and all patient reported measures from baseline, 6-month, 18-month, and 33-month surveys. It also contains individuals' unique provincial health number which will permit deterministic linkage to administrative health databases held by Alberta Health (including Alberta Precision Laboratory data, Pharmacy Information Network Data, Practitioner Claims data, Discharge Abstract Database, National Ambulatory Care Reporting System data). All PHNs were verified at the time of study enrollment to be sure that they were accurate and active. In cases where a deterministic linkage is not possible, probabilistic linkage using name, date of birth, and postal code will be used.

9. Interventions (s)

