10.1. Covariate Adjustment

Consistent with usual practice, we will only adjust the primary analysis for stratified variables (age (</>70; sex and low-income status) (48).

Assuming that randomization has worked, and we have approximately equal distribution of sociodemographic and clinic characteristics between randomization groups, we will not adjust our analyses for covariates, as this should have been dealt with through the process of randomization. If there is imbalance in important covariates between randomization groups, a sensitivity analysis will be conducted statistically adjusting for these imbalanced covariates through the modelling process.

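### EQ-5D is given a mixed model in section 6.3 and linear regression in section 10.5, with no precedence, no stated waves in 10.5 and no baseline score

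*Combined protocol and SAP*

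**What the plan says.** All section numbers are from the combined protocol and SAP unless stated otherwise.

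- **Outcome and timing.** Section 4.4 lists quality of life by EQ-5D-5L as a secondary outcome. Section 4.6 places the surveys at 6, 18 and 33 months. Section 8 (Data Sources) says that the trial database holds "all patient reported measures from baseline, 6-month, 18-month, and 33-month surveys".
- **Model in section 6.3.** "Mixed models will be used to compare EQ-5D index scores over time between the treatment groups for each intervention". Scores after death are set to 0.
- **Model in section 10.5.** "EQ5D index scores are continuous and will be analyzed using linear regression". No wave, summary measure, baseline term or handling of correlation is given.
- **Covariates, section 10.1.** The primary analysis is adjusted for the stratification variables only. On the assumption that randomisation has balanced the groups, the section adds: "we will not adjust our analyses for covariates". Imbalance would prompt a sensitivity analysis.
- **Missing EQ-5D data, section 6.3.** "In secondary analyses of EQ-5D index scores, to assess the impact of missing data, we will consider two alternate methods using imputation". The text continues: "Firstly, we will impute missing variables using multiple imputation as noted in section 10.3". Areas under the curve are then compared. The second method is: "Secondly, we will use last observation carried forward to impute missing values, and then similarly compare the area under the curve of index scores". Section 10.9 adds a complete-case analysis. Section 10.3 allows multiple imputation or full-information maximum likelihood under MAR, and MNAR sensitivity analyses if MAR is in doubt.
- **Status, section 5.2.** Secondary outcomes other than the components of the primary outcome are called exploratory and are not adjusted for multiplicity.

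The separate SAP deals with medication beliefs, self-efficacy and adherence. It does not analyse EQ-5D, so it does not settle which model applies.

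**The concern.** One outcome has two different analysis statements, and nothing ranks them. Section 10.5 is where a reader looks for the method of a secondary outcome. Section 6.3 gives the more specific statement and, by calling its imputation work secondary, implies that the mixed model is the main analysis. While both stand, the choice of model is open, and it is open for each of the two interventions.

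The choice matters because linear regression on an outcome measured several times can mean quite different things. It can use one wave, one summary per person, or all waves as separate rows. The first two give valid tests of different quantities. The third, with ordinary standard errors, overstates precision.

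A second gap is that neither section mentions the baseline EQ-5D score. Under section 10.1 it is not an adjustment variable, so a strong predictor of later scores that the trial already holds is left out.

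A smaller issue is that both imputation checks compare areas under the curve, whereas the main analysis is a mixed or linear model of scores. If a check disagreed with the main result, one could not tell whether missing data or the changed quantity was the cause.

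**Working it through.** **The plan's own figures.** The documents give no power, effect size, standard deviation or within-person correlation for EQ-5D. The sample size of 4714 in section 4.8 belongs to the primary rate outcome and does not bear on this point.

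**1. The two statements side by side.** Section 6.3 specifies mixed models, scores over time, and a comparison between groups for each intervention. Section 10.5 specifies linear regression and nothing more. They do not refer to each other.

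**2. What follows if the waves are pooled.** Inputs: m = 3 follow-up waves (sections 4.6 and 8) and alpha = 0.05 (section 5.1, taken as two-sided). The within-person correlation r is an assumption, shown over a range. Data are taken as complete, with the same correlation between any two waves. Ordinary least squares on all rows with model-based standard errors then gives:

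- design effect DE = 1 + (m − 1)r
- true SE ÷ reported SE = √DE
- actual type I error = 2[1 − Φ(1.96/√DE)]

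| r (assumed) | DE | √DE | 1.96/√DE | Type I error |
|---|---|---|---|---|
| 0.3 | 1.6 | 1.26 | 1.55 | 12.1% |
| 0.5 | 2.0 | 1.41 | 1.39 | 16.6% |
| 0.6 | 2.2 | 1.48 | 1.32 | 18.6% |
| 0.7 | 2.4 | 1.55 | 1.27 | 20.6% |

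A simulation under no effect (400 people in two equal groups, three waves, 4000 replicates) gave 13%, 17% and 20% at r = 0.3, 0.5 and 0.7.

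**3. What follows with one value per person.** In the same simulation, a test on the last visit alone, or on each person's mean over the three waves, rejected in 4.4% to 5.5% of replicates. The test is valid. It estimates a difference at one visit or in a summary, which need not be what section 6.3 intends by a comparison over time.

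**4. Baseline score.** For a single follow-up score with correlation r to baseline, adjustment removes a share r² of residual variance: 0.5² = 25% and 0.7² = 49%. These correlations are also assumed. The percentages should not be carried over to a three-wave model. The gain there depends on the correlation structure and may be smaller, for example where the mixed model already takes baseline as its first response. I have not quantified it.

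**5. Missing-data checks.** Last observation carried forward is the second of two imputation methods, and complete-case and conditional MNAR analyses are planned as well. It holds a surviving non-responder's score constant, which is a weak probe of outcome-related dropout. Section 10.3 acknowledges that such dropout may occur but fixes no MNAR scenario for EQ-5D.

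**The case against.** Section 10.5 can be read as a list of model families by type of variable: binary outcomes get log-binomial or logistic models, continuous ones get linear models. A linear mixed model belongs to the linear family, so section 6.3 would be the specific statement and section 10.5 the generic one. On that reading there is no second analysis. The reading is possible, but the documents do not state it. It also leaves out the time points, the contrast and the baseline term.

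A reader might infer that section 10.5 ignores repeated measurement and so produces standard errors that are too small. The text does not support this. It nowhere says that several rows per person enter the regression. Section 6.3 itself uses an area under the curve, one value per person, for which ordinary regression is valid.

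A reader might also infer that the missing-data assessment rests on last observation carried forward. It does not: multiple imputation comes first and other analyses are planned. Deaths are scored 0, so the constant-score assumption concerns survivors only.

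On baseline, the sentence in section 10.1 is conditional on successful randomisation, and a mixed model over time could include baseline as a response. Leaving baseline out costs precision and does not bias a randomised comparison. Section 10.3 could also bring in earlier measurements if they predict loss to follow-up, but only conditionally. These points limit the concern without supplying a specified baseline term.

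Finally, section 5.2 treats this outcome as exploratory, which lowers the stakes.

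**Conclusion.** The concern holds in a limited form. Sections 6.3 and 10.5 name different analyses for EQ-5D and neither takes precedence. Section 10.5 leaves the modelled waves and the handling of correlation unstated. The consequence ranges from none for type I error (one value per person, near 5%, but a different question) to about 17% to 21% (three waves pooled with model-based standard errors, r = 0.5 to 0.7). The upper end depends on a reading that the text does not state and on assumed correlations, so it shows what the gap allows. It does not describe what the plan does. Nor do the documents show that a model was chosen after results were seen.

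Not using baseline EQ-5D as a covariate is a loss of efficiency: 25% to 49% of residual variance for one follow-up score, at assumed correlations of 0.5 to 0.7. Last observation carried forward is a minor point about one supporting analysis. The change should be made, but it does not touch the primary outcome.

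**What to change.** Replace the EQ-5D sentence in section 10.5 with the section 6.3 model, written out in full and identical in both places:

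- a linear mixed model on the 6, 18 and 33-month index scores with within-person correlation;
- terms for arm, time and arm by time, the other factorial intervention, baseline EQ-5D and the stratification variables;
- one named main contrast, for example the average difference over follow-up;
- a statement of how zeros after death enter the model.

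For missing data, label last observation carried forward as supplementary, or replace it with delta-adjusted multiple imputation. Apply the sensitivity analyses to the same quantity as the main model, and keep area under the curve as a separately labelled analysis if it is wanted. Section 9.1 plans multiple imputation of patient-reported outcomes after withdrawal, while section 6.3 places imputation of EQ-5D among secondary analyses. State which applies to the main model.

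The cost is wording, and no new data are needed. Sections 4.11 and 4.12 schedule the analyses for 2022, and the separate SAP's introduction already reports main trial findings, so the change may no longer be prospective. The documents do not say whether EQ-5D has been analysed. If it has, report which model was treated as main and label the other as supplementary.

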10.6. Analysis Methods- Exploratory Outcomes and Analyses

In addition to the primary analysis, we will conduct time-to- first event analysis and will use cox regression models to calculate Hazards Ratios separately for each of these outcomes:

- Mortality
- MACE: Non-fatal MI, Non-fatal Stroke, CV death

- ACSC hospitalization

10.7. Safety

Given the low-risk nature of our interventions, and since our outcomes will be assessed using administrative data (with a one-year lag to receipt of data), there will be no external data safety and monitoring board. This study is considered low risk since patients' physicians remain ultimately responsible for managing patients' medical treatments and any complications that may arise as part of their treatment.

10.8. Planned Subgroup Analyses

We have a priori specified particular subgroup analyses, considering the biological plausibility for subgroups. We will conduct analyses stratified by subgroup, as described in the primary and secondary outcomes sections. We will provide effects with confidence intervals for subgroups (rather than p-values), as tests of interactions for subgroups can fail to detect important effects. These will be presented in a forest plot (49,50).

The subgroups of interest include:

Gender: Men vs Women (self-reported), likely exclude gender diverse

Age: >70 years vs 65-69 years

Income group: <30,000 vs >30,000

Financial barriers: Present vs Absent

Condition type: Diabetes // CKD // ASCVD // Risk factors only

Multimorbidity: 1-2 vs 3-4 indicated conditions

Primary Care Relational Continuity: Low/Medium vs High

Specialist Involvement in the year prior to randomization: Yes vs No

On statin at baseline: Yes vs No

On ACE/ARB at baseline: Yes vs No

Living environment: supported living vs. Independent living

Baseline medication adherence: >80% PDC for all covered meds vs <80% for any covered med

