### 7.4. Subgroup analyses

We have specified the subgroups below to conduct analyses with stratifications. We will calculate the effect and confidence interval for each subset. We included subgroup analysis because there may be a subgroup that would benefit more from these interventions.

- a. Age: >70 years vs 65-69 years
- b. Income group: <30,000 vs >30,000
- c. Financial barriers: Present vs Absent
- d. Condition type: Diabetes // CKD // ASCVD // Risk factors only
- e. Multimorbidity: 1-2 vs 3-4 indicated conditions
- f. Primary Care Relational Continuity: Low/Medium vs High
- g. Specialist Involvement in the Year Before Randomization: Yes vs No
- h. On statin at baseline: Yes vs No
- i. On ACE/ARB at baseline: Yes vs No
- j. Living environment: supported living vs. Independent living
- k. Urban / rural

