5.1. Confidence Intervals and P-values

In all our analyses, we will calculate 95% Confidence intervals around all point estimates and will calculate p-values using appropriate statistical tests. We will consider our alpha value to be 0.05.

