10.9. Sensitivity Analyses

Sensitivity analyses will be conducted as follows:

- Excluding those who have admissions/costs in the top 1% of all participants
- Excluding participants who resided in the same household as another participant.
- We will also conduct a complete case analysis to examine the effects of the missing data, where relevant (ie. Self-reported outcomes).

11. Interaction between intervention arms

Given the factorial design of the trial, we will assess for multiplicative interaction. Because each of our two interventions was designed to address very different patient barriers to

medication adherence (financial barriers vs. Knowledge/motivation), we don't anticipate major multiplicative interaction effects.

12. Health Economic Analysis

The primary outcome will be mean total 3-year in-study health care costs for patients receiving copayment elimination (or not) and those receiving MOXIE (or not), adjusting for co-intervention received. We will include costs for hospitalization and ED visits, physician claims (specialist and primary care physician visit and procedure billing costs), prescription medications (including those subject and not subject to copayment elimination), nonphysician ambulatory costs (day medicine and day surgery clinics), and outpatient diagnostic imaging and laboratory costs. The total costs will be calculated as the sum of these costs. Alberta Health uses Canadian Institute of Health Information case-mix grouper methods to estimate hospital costs and ambulatory-case costing methods to estimate outpatient costs.

Physician claims will be based on the amount paid by Alberta Health. The cost of medications will be estimated by combining a database containing a comprehensive list of medications dispensed to all Alberta residents with a price list from Alberta Blue Cross, including dispensing fee. Diagnostic imaging and laboratory costs will be based on estimates provided by Alberta Health Services. All costs will be reported in 2021 Canadian dollars.

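### Neither document plans a treatment-by-subgroup estimate, so the SAP's question of whether a subgroup gains more from the interventions is never estimated

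*Combined protocol and SAP*

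**What the plan says.** Section 10.8 of the Combined protocol and SAP lists 12 subgroup factors. It plans separate analyses by stratum ("We will conduct analyses stratified by subgroup, as described in the primary and secondary outcomes sections") and chooses what to report as follows: "We will provide effects with confidence intervals for subgroups (rather than p-values), as tests of interactions for subgroups can fail to detect important effects". On display it says "These will be presented in a forest plot".

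Section 7.4 of the SAP lists 11 factors, a to k, and plans the same output: "We will calculate the effect and confidence interval for each subset". It gives its purpose directly: "We included subgroup analysis because there may be a subgroup that would benefit more from these interventions".

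The only interaction that either document sets out to assess is in section 11 of the Combined protocol and SAP: "Given the factorial design of the trial, we will assess for multiplicative interaction". That is the interaction between the two interventions. It is not an interaction of an intervention with a subgroup.

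**The concern.** Whether one stratum benefits more than another is a question about the difference (or ratio) of two effects. A separate interval in each stratum says how well each effect is known, but it does not estimate the contrast. The plan is right that interaction tests have little power here. Dropping the contrast does not cure that, because the stratum intervals carry the same limited information about the difference and do not display it.

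With no contrast on the page, the easiest comparison is whether one interval excludes 1 while its neighbour includes it. Nothing in either document warns against this. Section 6.1 of the SAP applies p-values and a 0.05 threshold to all analyses, and section 7.4 does not exempt subgroups. There are 24 strata in the SAP and 26 in the Combined protocol and SAP, for two interventions and several outcomes, so there is ample room for chance patterns. A statement about who gains from removing copayments could bear on coverage decisions.

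**Working it through.** **Inputs** (Combined protocol and SAP, sections 4.8 and 5.1): control rate r0 = 0.14 per participant-year, rate ratio RR = 0.88, follow-up T = 3 years, 1:1 allocation (p = 0.5), 80% power, alpha 0.05, 95% intervals. Sidedness is not stated. The documents give no subgroup sizes, so I assume 50:50 and show the range to 90:10.

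**1. Reproduce the plan's sample size.** Poisson-regression formula for a binary covariate, two-sided alpha:

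N = [1.960·√(1/(p(1−p))) + 0.8416·√(1/(1−p) + 1/(p·RR))]² / (T·r0·(ln RR)²)

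- Numerator: (1.960 × 2 + 0.8416 × 2.0671)² = (3.920 + 1.740)² = 32.03.
- Denominator: 3 × 0.14 × 0.01634 = 0.006863.
- N = 4667, and 4667 × 1.01 = 4713.67, or 4714. Both match section 4.8. One-sided alpha would give 3686, so the plan's alpha is two-sided.

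**2. Chance of a discordant pair with the same true effect in both strata.** The overall expected z is 1.960 + 0.842 = 2.802. A stratum holding share f of the information has expected z of 2.802·√f and power P = Φ(2.802√f − 1.96) + Φ(−2.802√f − 1.96). The chance that exactly one interval excludes 1 is P1(1 − P2) + P2(1 − P1).

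| Split | Power in each stratum | Exactly one excludes 1 |
|---|---|---|
| 50:50 | 0.508, 0.508 | 50.0% |
| 60:40 | 0.583, 0.425 | 51.2% |
| 70:30 | 0.650, 0.335 | 54.9% |
| 80:20 | 0.707, 0.240 | 60.8% |
| 90:10 | 0.757, 0.144 | 68.3% |

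A simulation of the 50:50 case (400,000 replicates) gave 50.1%.

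**3. Other true effects, 50:50 split, N = 4714, Wald test on the log rate ratio.**

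- RR 0.94: overall z = 1.355, stratum power 0.160, so 2 × 0.160 × 0.840 = 26.9%.
- RR 0.90: 46.3%. RR 0.85: 42.9%. RR 0.80: 16.1%.
- No effect: 2 × 0.05 × 0.95 = 9.5%, for any split.

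**4. Overdispersion at the design effect, 50:50.** Expected z is divided by the square root of an assumed variance factor.

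- Factor 1.5: 46.4%. Factor 2: stratum power 0.288, so 2 × 0.288 × 0.712 = 41.0%. Factor 3: 33.0%.
- Section 4.8 suggests a factor near 2. Its mean of 0.14 × 3 = 0.42 events implies 1 − e^(−0.42) = 34% with any event under a Poisson model, but it reports 26%. A negative binomial that fits both has (1 + 0.42/k)^(−k) = 0.74, so k ≈ 0.47 and a variance factor of 1 + 0.42/k ≈ 1.9. The result is then about 42%. This is approximate, because the 26% figure does not list revascularization.

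**5. A stricter reading.** If the reader requires non-overlapping intervals, the chance is 2[1 − Φ(1.96(s1 + s2)/√(s1² + s2²))], with each s the stratum's standard error. This is 0.6% at 50:50 and 1.3% at 90:10.

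**6. The interaction contrast.** With no true difference, its 95% interval excludes 1 in 5% of trials (simulation 4.99%). At 50:50 its standard error is 1/√(0.5 × 0.5) = 2.0 times the overall one. For an interaction as large as the design effect, the expected z is 2.802/2 = 1.401 and power is Φ(1.401 − 1.96) ≈ 29%.

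**The case against.** The strongest reply is that the documents never say a differential effect will be declared when one interval excludes 1 and another does not. Section 10.8 of the Combined protocol and SAP moves away from p-values for subgroups. Any error therefore belongs to an assumed reader, and a reader who looks for non-overlapping intervals would be misled only about 1% of the time. This stands: the 50% figure describes a common misreading and not a planned decision rule. It does not supply the missing contrast.

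Second, the two halves of the argument come from different documents. Only the SAP states the aim of finding a subgroup that gains more, and only the Combined protocol and SAP gives the low-power reason. That is correct, but the planned output is the same in both, and neither contains the contrast.

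Third, for non-overlapping strata a reader can recover the contrast from the forest plot. One takes the difference of the log effects, with each standard error equal to ln(upper/lower)/(2 × 1.96). This limits the harm, but it leaves the comparison to each reader.

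Fourth, when both strata truly benefit, a discordant pair is one correct detection and one miss. It becomes a false claim only if someone infers a difference from it. This is also right.

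A reader might further infer that about half of the SAP's 11 factors would show a spurious pattern. The documents do not support that. The 80% power is for the composite event rate, whereas the SAP's outcomes are BMQ, MASES and PDC. Section 5.6 of the SAP only repeats the trial's sample size. Condition type also has four levels, so the two-stratum formula does not apply to it.

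**Conclusion.** The point holds in conditional form. No treatment-by-subgroup estimate is planned in either document, and the comparison that section 7.4 of the SAP sets out to make is therefore not estimated. The remark on low power is accurate (about 29% for an interaction as large as the design effect at a 50:50 split), but it argues for showing a wide interval, not for omitting it.

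The size depends on how the intervals are read and on the true effect. For the primary outcome, two equal strata and a reading by which interval excludes 1, the chance of an apparent difference where none exists is about 50% at the design effect, 27% at RR 0.94, 41% at the design effect with doubled variance, and 9.5% with no effect. The interaction contrast gives 5%. Uneven splits raise the design-effect figure, to 68% at 90:10. A larger true effect can lower it, to 16% at RR 0.80 with equal strata.

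Two stronger statements are tempting and go too far: that the plan produces false subgroup differences half the time in general, and that it prescribes the faulty reading. The first drops the conditions, and the second is not in the text. No numerical error rate can be given for the BMQ, MASES and PDC analyses.

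**What to change.** For each factor with mutually exclusive levels, fit one model with a treatment-by-subgroup term. Show the ratio of rate ratios or risk ratios with its 95% interval beside the stratum estimates on the forest plot. For factors with more than two levels, add a global heterogeneity estimate. Condition type needs separate handling, because the documents do not say that its four categories are exclusive and the multimorbidity factor allows several conditions per person. Either define exclusive categories, or fit a separate yes/no interaction term for each condition.

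Add one sentence to both subgroup sections: any claim of differential benefit rests on this contrast and not on which within-subgroup interval excludes 1. Reporting the contrast as an estimate with an interval keeps to the plan's preference for intervals over p-values.

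The cost is a little extra modelling and a column on the plot, with no new data. The interaction intervals will be wide, and most will be inconclusive. With 12 factors, about 12 × 0.05 = 0.6 contrasts per intervention and outcome would still exclude 1 by chance, so the results should be labelled exploratory.
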